8.5.1.1. Criteria for Handling Concentrations Below the Limit of Quantification

Predose concentration values that are below the level of quantification (BLQ) will be set to 0 and postdose concentration values that are BLQ will be set to missing for the purposes of PK analysis, with defined exceptions as follows;

- If there are late positive concentration values following 2 BLQ concentration values in the apparent terminal phase, these values will be evaluated. If these values are considered to be anomalous, they will be set to missing.
- If an entire plasma/blood concentration-time profile is BLQ, the profile will be excluded from the PK analysis.
- If a predose plasma/blood concentration is missing, this value will be set to 0 by default.

8.5.1.2. Criteria for the Regression Analysis of the Terminal Elimination Phase

- At least 3 data points will be included in the regression analysis and preferably should not include C_{max} .
- When assessing terminal elimination phases, the adjusted coefficient of determination for exponential fit (R^2 -adj) will be used as a measure of the goodness of fit of the data points to the determined line.
- The λ_z will not be assigned if the R^2 -adj value of the regression line is <0.8. In cases where the λ_z is not assigned all regression based parameters (including R^2 -adj) will not be calculated.
- Time period used for the estimation of $t_{1/2,z}$ will be calculated over a time period of at least 2 half-lives (λ_z Span Ratio >2), where possible. Where λ_z Span Ratio <2 the robustness of $t_{1/2,z}$ will be discussed in the CSR.

8.5.1.3. Calculation of Area Under the Concentration-time Curve

- The minimum requirement for the calculation of AUC will be the inclusion of at least 3 consecutive concentrations above the lower limit of quantification (LLOQ), with at least 1 of these concentrations following C_{max} .
- AUCs will be calculated using the Linear Trapezoidal Linear/Log Interpolation method.

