1.3 Schedule of Assessments

| Table 1.3-1 | | Schedule of Assessments | | | | |
|---|-----------------------------------|-------------------------|--|----------------|--|--|
| Period | Screening Day -28 to Day -2 | Check-in Day -1 | Days 1 to 8 | | Discharge ^a Days 9 to 10 | Outpatient Visits ^b Days 11 to 12 |
| ENTRANCE/HISTORY | | | | | | |
| Informed consent | X | | | | | |
| Demographics | X | | | | | |
| Inclusion/Exclusion Criteria | X | X | | | | |
| Medical history | X | X ^c | | | | |
| Urine drug screen | X | X | | | | |
| Alcohol breath test | X | X | | | | |
| Serology | X | | | | | |
| Height and body weight | X ^d | X ^e | 24 and 48 hours after the start of infusion ^e | | | |
| INVESTIGATIONAL MEDICINAL PRODUCT ADMINISTRATION | | | | | | |
| (¹⁴ C)-OPC-61815 | | | Day 1 (0 hours) | | | |
| PHARMACOKINETICS | | | | | | |
| Blood sampling for OPC-61815 free form and OPC-41061 concentration (plasma) | | | Predose and 1 hour (end of infusion), and 1.5, 2, 3, 4, 6, 12, 24, and 48 hours after the start of infusion | | | |
| Blood sampling for total radioactivity (whole blood and plasma) | | | Predose and 1 hour (end of infusion), and 1.5, 2, 3, 4, 6, 12, 24, 48, 72, 96, 120, 144, and 168 hours after the start of infusion | X ^a | | |

Table 1.3-1 Schedule of Assessments

| | | | | | |
|--|---|----------------|---|-------------------|----------------|
| Blood sampling for metabolite profiling and identification (plasma) | | | Predose and 1 hour (end of infusion), and 1.5, 2, 3, 4, 6, 12, 24, 48, 72, 96, 120, 144, and 168 hours after the start of infusion | | |
| Urine collection for total radioactivity and metabolite profiling and identification | | | Predose (from Check-in to 0 hours) and 0 to 24, 24 to 48, 48 to 72, 72 to 96, 96 to 120, 120 to 144, and 144 to 168 hours after the start of infusion | X ^a | X ^b |
| Feces collection for total radioactivity and metabolite profiling and identification | | | Predose (from Check-in to 0 hours) and 0 to 24, 24 to 48, 48 to 72, 72 to 96, 96 to 120, 120 to 144, and 144 to 168 hours after the start of infusion | X ^a | X ^b |
| SAFETY | | | | | |
| Adverse event recording | X | X | Ongoing | X | X |
| Prior/concomitant medication monitoring | X | X | Ongoing | X | X |
| Clinical laboratory evaluations | X | X | 1.5 ⁱ , 24, and 48 hours after start of infusion | X ^g | |
| Physical examination | X | X ^f | 1.5, 24, and 48 hours after start of infusion ^f | X ^{f, h} | |

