When (^{14}C)-OPC-61815 was incubated with human liver, kidney, lung, and small intestine 9000 g supernatant fractions (S9), OPC-61815 underwent hydrolysis to OPC-41061. OPC-61815 also underwent hydrolysis to OPC-41061 when incubated with human-derived acid phosphatase and alkaline phosphatase. In an investigation of the in vitro metabolism of OPC-61815 by human liver S9 fraction and human hepatocytes, all metabolites detected were the same as those of OPC-41061, and no metabolite with a phosphate group was detected in the metabolic reaction of (^{14}C)-OPC-61815 with human liver S9 fraction.

Following a single IV dose of (^{14}C)-OPC-61815 at 12.75 mg/kg to male and female rats, the urinary and fecal excretion of radioactivity up to 168 hours postdose was 4.59% and 91.08%, respectively, in male rats, and 4.74% and 93.26%, respectively, in female rats, showing that the radioactivity administered was excreted mainly in feces. The biliary excretion of radioactivity was 92.2% in male rats and 91.5% in female rats. In male rats, 61.0% of the radioactivity administered was resorbed via enterohepatic circulation. No obvious sex difference was noted in urinary, fecal, or biliary excretion in rats. Following

a single IV dose of (¹⁴C)-OPC-61815 at 3.825 mg/kg to male dogs, the urinary and fecal excretion of radioactivity up to 168 hours postdose was 5.32% and 89.50%, respectively.

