
2.4.2 Pharmacokinetics

Pharmacokinetic data for OPC-61815 free form following single and multiple IV doses is presented in the table below. The PK data for OPC-61815 free form following 1- and 5-minute infusions is available in the IB¹, along with PK data for OPC-41061 and major metabolites for all studies.

Table 2.4.2-1 Pharmacokinetic Data for OPC-61815 Free Form

| Dose (mg) | AUC _∞ (ng.h/mL) | AUC _t (ng.h/mL) | C _{max} (ng/mL) | t _{max} (h) ^a | t _{1/2} (h) |
|--|-------------------------------|-------------------------------|-----------------------------|--------------------------------------|-------------------------|
| Single IV dose – Mean (SD) | | | | | |
| 0.3 mg | - | 7.803 (8.170) | 53.02 (29.28) | 0.020 (0-0.25) | - |
| 1 mg | 175.0 (-) | 85.90 (21.91) | 182.2 (21.72) | 0.000 (0-0.25) | 0.7170 (0-0) |
| 3 mg | 427.2 (61.14) | 374.3 (52.91) | 559.5 (85.52) | 0.000 (0-0.02) | 0.6335 (0.1065) |
| 7.5 mg | 1242 (182.2) | 1144 (171.1) | 1832 (294.2) | 0 (0-0) | 1.172 (0.2819) |
| 15 mg | 3008 (416.6) | 2868 (362.3) | 3348 (637.7) | 0.000 (0-0.25) | 1.730 (0.3279) |
| 30 mg | 4882 (817.9) | 4727 (839.9) | 7670 (755.3) | 0 (0-0) | 1.683 (0.4837) |
| Multiple IV dose – Day 1: Mean (SD) | | | | | |
| 1.25 mg | 211.8 (32.11) | 167.3 (32.55) | 371.8 (78.15) | 3.0 (3-3) | 0.5308 (0.1074) |
| 5 mg | 886.7 (140.8) | 784.0 (150.2) | 1165 (394.4) | 3.0 (3-15) | 1.193 (0.3741) |
| 20 mg | 3379 (492.8) | 3178 (400.1) | 4351 (1496) | 3.0 (3-15) | 2.510 (1.927) |
| Multiple IV dose – Day 9: Mean (SD) | | | | | |
| 1.25 mg | 169.0 (33.05) ^b | - | 320.0 (89.42) | 3.0 (3-15) | 0.5748 (0.1549) |
| 5 mg | 924.8 (136.9) ^b | - | 1375 (368.4) | 3.0 (3-3) | 1.329 (0.4530) |
| 20 mg | 3416 (344.7) ^b | - | 4137 (955.7) | 3.0 (3-15) | 2.419 (1.145) |

Abbreviations: AUC_∞ = area under the concentration-time curve from time zero to infinity; AUC_t = area under the concentration-time curve calculated to the last observable concentration at time t; AUC_{24h} = area under the concentration-time curve from time zero until 24 hours postdose; C_{max} = maximum peak concentration; IV = intravenous; t_{max} = time to maximum peak concentration; t_{1/2} = elimination half-life.

^a median (min-max)

^b AUC_{24h}

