4. STUDY DESIGN

This will be a Phase I, single-site, open-label, nonrandomized, single IV dose trial in healthy male Japanese subjects.

Potential subjects will be screened to assess their eligibility to enter the trial within 28 days prior to the dose administration. Subjects will be enrolled and admitted into the trial site on Day -1. On Day 1, all subjects will receive a single IV infusion of 16 mg (¹⁴C)-OPC-61815, containing approximately 75.1 µCi (2.78 MBq), over 60 minutes (55 to 65 minutes, inclusive) in the fasted state.

It is planned for at least 8 subjects to be dosed to ensure that 6 subjects complete the IV infusion. Up to a maximum of 10 subjects will be dosed in total.

Subjects will be confined to the trial site until at least Day 9. Subjects will be discharged from the trial site on Day 9 if the following discharge criteria are met:

- $\geq 90\%$ mass balance recovery, and/or
- < 1% of the total radioactive dose is recovered in combined excreta (urine and feces) in 2 consecutive 24-hour periods.

If these criteria are not met by Day 9, subjects will remain at the trial site until any one of the discharge criterion are met up to a maximum of Day 10 to continue 24-hour blood, urine, and feces collections for total radioactivity, unless otherwise agreed upon by the sponsor and investigator.

[figure not shown]
If criteria are not met by Day 10, subjects may be asked to collect 24-hour excreta samples on up to 2 further occasions on a nonresidential basis to allow extrapolation of urinary and fecal excretion. If needed, the 2 additional 24-hour nonresidential collections will start on Days 10 and 11 (to be brought to the trial site at the end of the collection interval on Days 11 and 12, respectively). If on the second occasion the subject has still not met the desired criterion, then the subject will be discharged from the trial, per investigator and sponsor decision.

Final Discharge from trial will be day of discharge from residential treatment period or the day of last outpatient visit if required to attend them based on the discharge criteria. The total duration of trial participation for each subject (from Screening through Final Discharge from trial) is anticipated to be a maximum of approximately 40 days.

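### The SAP's AUC rule, read as linear throughout, overstates AUC of OPC-41061 and total radioactivity by a few percent on the late sampling gaps; linear-up/log-down is a cheap improvement

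*SAP*

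**What the plan says.** SAP section 8.5.1.3 sets one rule for every AUC: "AUCs will be calculated using the Linear Trapezoidal Linear/Log Interpolation method". The rule is not explained further. The parameter table in SAP 8.5.1 lists AUCt and AUC∞ but no AUC over a fixed partial interval, which is where an interpolated concentration would be needed.

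Protocol Table 1.3-1 samples OPC-61815 free form and OPC-41061 at "Predose and 1 hour (end of infusion), and 1.5, 2, 3, 4, 6, 12, 24, and 48 hours after the start of infusion". Whole blood and plasma radioactivity are sampled at "Predose and 1 hour (end of infusion), and 1.5, 2, 3, 4, 6, 12, 24, 48, 72, 96, 120, 144, and 168 hours". The infusion runs "over 60 minutes (55 to 65 minutes, inclusive) in the fasted state" (SAP section 4).

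Under SAP 8.5.1.1, "postdose concentration values that are BLQ will be set to missing for the purposes of PK analysis", so the LLOQ decides which late gaps enter AUCt. SAP 3.1 makes AUCt and AUC∞ primary endpoints for both plasma analytes and for total radioactivity in plasma and whole blood.

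**The concern.** During exponential decline the curve lies below the straight line joining two samples, so a linear trapezoid is too large over that interval. The excess grows quickly with the ratio of gap to half-life. The last gaps here are 6, 12 and 24 h, and the radioactivity schedule then continues in 24 h steps.

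At stake is a systematic upward error in AUCs that are primary endpoints. It does not shrink with more subjects, and its size differs between analytes because it depends on curve shape. Separately, an undefined method name leaves room for two analysts to apply different rules.

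**Working it through.** The plan states no figure for AUC error, so there is none to reproduce.

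**Inputs from the documents.** Sampling times, 1 h infusion, AUC rule and BLQ rule as above. Parent mean half-life is 1.730 h at 15 mg and 2.510 h at 20 mg on Day 1 (Protocol Table 2.4.2-1).

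**Assumed, because the documents do not give them.**
- OPC-41061: elimination half-life 3 to 12 h (extended to 24 h) and formation half-life 0.5 to 2.5 h. Protocol 2.4.2 leaves these data to the Investigator's Brochure ("along with PK data for OPC-41061 and major metabolites for all studies").
- Total radioactivity: biexponential, fast phase 1.7 to 6 h, slow phase 12 to 180 h, slow share 5 to 30% of the initial level. A slow tail is plausible given the rat finding: "In male rats, 61.0% of the radioactivity administered was resorbed via enterohepatic circulation".
- LLOQ: 0.1 to 1% of peak, with 5% as a stress case.

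**One gap.** For gap g and rate λ = ln 2 / half-life, linear/exact = (λg/2)(1 + e^(−λg))/(1 − e^(−λg)). At a 6 h half-life:
- 6 h gap: 0.3466 × 1.5/0.5 = 1.040, or +4.0%
- 12 h gap: 0.6931 × 1.25/0.75 = 1.155, or +15.5%
- 24 h gap: 1.3863 × 1.0625/0.9375 = 1.571, or +57%

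**One whole profile.** OPC-41061 with formation half-life 1 h (kf = 0.6931) and elimination half-life 6 h (ke = 0.1155), unit dose scale, error-free. After the infusion, C(t) = Σ (Aᵢ/kᵢ)(1 − e^(−kᵢ)) e^(−kᵢ(t−1)), with A = ±kf/(kf − ke) = ±1.2 for ke and kf respectively. This gives 0.6931 at 4 h (the sampled peak), then 0.6090, 0.3176, 0.0795 and 0.0050 at 6, 12, 24 and 48 h. The linear area is g(C₁ + C₂)/2. The log area is g(C₁ − C₂)/ln(C₁/C₂).

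| Interval | Exact | Linear | Linear-up/log-down |
|---|---|---|---|
| 0–6 h | 3.190 | 3.194 | 3.192 |
| 6–12 h | 2.714 | 2.780 | 2.686 |
| 12–24 h | 2.064 | 2.383 | 2.063 |
| 24–48 h | 0.645 | 1.014 | 0.645 |
| Total | 8.613 | 9.370 | 8.586 |

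The AUCt error is 9.370/8.613 − 1 = +8.8% linear and 8.586/8.613 − 1 = −0.3% log-down. The 48 h value is 0.0050/0.6931 = 0.7% of peak. With the LLOQ at 1% of peak that sample drops out, and the linear error falls to (9.370 − 1.014)/(8.613 − 0.645) − 1 = +4.9%.

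**Across the assumed ranges, OPC-41061.**
- AUCt, half-life 3 to 12 h, LLOQ 0.1 to 1% of peak: linear +3.7 to +9.5%; log-down −2.6 to +0.6%.
- AUC∞, same half-lives and LLOQ: linear +4.0 to +9.5%; log-down −1.7 to +0.6%, closer to the truth in every scenario.
- AUCt, half-life 16 to 24 h (formation half-life 0.5 and 1.7 h, LLOQ 0.5%): linear +1.2 to +3.4%.
- AUCt, half-life 3 to 12 h, LLOQ 5% of peak: linear about 0 to +6.6%.

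**Total radioactivity, AUCt, LLOQ 0.5% of peak.**

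| Slow half-life | Linear | Linear-up/log-down |
|---|---|---|
| 12 h | +5.0 to +7.4% | +0.2 to +1.4% |
| 24 h | +2.8 to +7.0% | +0.6 to +1.8% |
| 48 h | +1.2 to +6.0% | +0.4 to +1.8% |
| 100 h | +0.5 to +5.0% | +0.3 to +1.9% |
| 180 h | +0.3 to +4.5% | +0.2 to +1.9% |

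Log-down removes a median of about 63% of the linear error, and at least about 27%. For AUC∞ it was closer to the truth in about 95% of scenarios. A counter-example: fast phase 3 h, slow phase 12 h, slow share 10%, LLOQ 1% gives +1.1% linear and −3.1% log-down.

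**Parent.** With a monoexponential curve at 1.7 to 2.5 h and LLOQ 0.5% of peak, linear gives +4.6% to +4.1% and log-down about −1.1% to −0.6%. With biexponential curves matched to Table 2.4.2-1, linear ranges from −6.4 to +7.1% and log-down from −10 to −0.6%. With no sample between predose and 1 h, the chord over the infusion can be too low, and this may offset the late excess.

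**The case against.** The linear rule is prespecified and legitimate, the analyses are descriptive, and the error is modest beside between-subject spread (parent AUC∞ CV at 15 mg is 416.6/3008 = 14%). It also partly cancels in the blood/plasma AUC ratios if the two curves have similar shapes. All of that stands and sets the priority low. It does not make the linear rule the better choice, because the error is systematic.

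Three stronger readings are tempting, and the documents do not support them.
- A reader might infer a fixed overstatement of several percent for every analyte. The sizes rest on half-lives and an LLOQ that the documents do not give, and for radioactivity the error can be close to zero when a long slow phase dominates.
- A reader might infer that every late gap spans at least one half-life. It need not: with a 12 h half-life the 6–12 h gap is half of one, and with a 100 h slow phase a 24 h step is about a quarter.
- A reader might infer that the 10% threshold for identifying metabolites is distorted. SAP 3.1 and 8.5.1 place that calculation in a separate metabolite profiling report, and nothing says that 8.5.1.3 governs its AUCs.

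The method name could also be taken to mean linear-up/log-down already. If that is intended, the numerical concern falls away and only the need to say so remains.

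**Conclusion.** The concern holds as a low-priority improvement. If areas are linear throughout, AUC is overstated by about 4 to 9% for OPC-41061, provided its half-life is 3 to 12 h and the LLOQ is at most 1% of peak. The overstatement is about 1 to 3% at 16 to 24 h. For total radioactivity it is about 0 to 7%, smallest when a long slow phase dominates.

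Linear-up/log-down brings AUCt to within about 2 to 3% for OPC-41061 and about 0 to 2% for total radioactivity. For AUC∞ of radioactivity it is better in most scenarios, but not all. The upward direction over a declining interval is mathematical; the sizes are for error-free assumed curves. For the parent, the better rule cannot be settled from the documents. Mass balance and excretion results are unaffected, since they do not use AUC.

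**What to change.** In SAP 8.5.1.3, replace the method name with an explicit rule: AUCs of OPC-41061, and of total radioactivity in plasma and whole blood, use the linear trapezoid where concentrations rise or stay level and the logarithmic trapezoid where they fall. Wording it by direction also covers a second rise after Cmax, which recirculation could cause.

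For OPC-61815 free form, state the chosen rule and the reason, taking account of the expected curve shape and the lack of a mid-infusion sample.

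If the linear rule is kept for any analyte, give the reason. The half-lives in the Investigator's Brochure and the assay LLOQs would let the sponsor size the error directly.

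The cost is one or two SAP sentences before database lock and a software setting, with no extra samples. The downside is small: AUCs are less directly comparable with earlier studies if those used the linear rule.

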8.5.1.4. Anomalous Values

- If a value is considered to be anomalous due to being inconsistent with the expected PK profile, it may be appropriate to exclude this point from the PK analysis. However, the exclusion of data must have strong justification and will be documented in the raw data and the CSR.

8.5.2. Presentation of Pharmacokinetic Data

8.5.2.1. Presentation Pharmacokinetic Concentration Data

- The following rules will be applied if there are values that are BLQ or if there are missing values (eg, no result [NR] or No Sample [NS]) in a concentration data series to be summarized:
 - For the calculation of summary statistics, predose BLQ values will be set to zero and postdose BLQ values will be set to missing.
 - If an embedded BLQ value is considered anomalous within the concentration-time profile, this value will be excluded from the summary statistics.
 - Where there is NR or NS, these will be set to missing.
 - If there are less than 3 non-missing values in the data series, only the min, max and n will be presented. The other summary statistics will be denoted as not calculated (NC).

Where there is a PK blood sampling time deviation from the nominal sampling time occurring outside the PK sampling time windows specified in the protocol, the concentration will be excluded from the summary statistics and summary concentration-time figures and flagged in the concentration listings.

8.5.2.2. Presentation Pharmacokinetic Parameters

Individual PK parameters will be presented to 3 significant figures with the exception of t_{max} , t_{last} , λ_z Lower and λ_z Upper which will be presented to 2 decimal places.

For the calculation of summary statistics of PK parameters, all NR and NC values in a data series will be set to missing.

The AUC values will be set to NC if they have been calculated using fewer than 3 concentrations, and/or 3 concentrations if the last is C_{max} .

8.5.3. Pharmacokinetic Statistical Methodology

All PK concentrations and parameters will be listed.

Summary tables, mean (+ SD) figures, overlaying individual figures, and individual figures by time postdose will be provided for plasma PK concentrations. All figures will be produced

on both linear and semi-logarithmic scales. The +SD bars will be only displayed on the linear scale.

Summary tables will be provided for all PK parameters, with the exception of regression-related PK parameters.

No inferential statistical analyses are planned.

8.6. Safety and Tolerability Assessments

8.6.1. Adverse Events

All AEs will be coded using the Medical Dictionary for Regulatory Activities (MedDRA) Version 22.1 (or higher if upversioned during the study).

A treatment-emergent adverse event (TEAE) will be defined as an AE that starts during or after the start of the infusion, or starts prior to the start of the infusion and increases in severity after the start of the infusion.

A treatment-related TEAE will be defined as a TEAE with a relationship of related to the study treatment, as determined by the investigator.

All AEs will be listed. In addition to the data recorded in the database, the listings will include derived onset time and duration. Onset time will be calculated from the time of the start of the infusion for TEAEs only.

The frequency of subjects with TEAEs and the number of TEAEs will be summarized for the following categories:

- TEAEs (overall, serious, leading to discontinuation of study treatment, and leading to death)
- TEAEs by severity
- Treatment-related TEAEs (overall, serious, leading to discontinuation of study treatment, and leading to death)
- Treatment-related TEAEs by severity

The frequency of subjects will be summarized separately for TEAEs and treatment-related TEAEs by the following:

- System organ class, and preferred term (PT)
- PT

For the AE data the following rules will apply:

- For the derivation of TEAE status: If the start date/time of an AE is incomplete or missing, a AE will be assumed to be a TEAE, unless the incomplete start date/time or the end date/time indicates a AE started prior to the start of the infusion.
- For the derivation of treatment-related TEAE status: If the study treatment relationship for a TEAE is missing, a TEAE will be assumed to be a treatment-related TEAE.
- For the derivation of onset time: If the start date/time of an AE is missing, onset time will not be calculated. If the start date/time of an AE is incomplete, where possible, the minimum possible onset time will be calculated and presented in ‘ \geq DD:HH:MM’ format (eg, if the date/time of the start of the infusion is 01MAY2019/08:00 and recorded start date/time of an AE is 03MAY2019, then the minimum possible onset time will be calculated by assuming the AE started at the first hour and minute of 03MAY2019 [03MAY2019/00:00], thus will be presented as onset time \geq 01:16:00 in the listing).
- For the derivation of duration: If the end date/time of an AE is missing, duration will not be calculated. If the start or end date/time of an AE is incomplete, where possible, the maximum possible duration will be calculated and presented in ‘ \leq DD:HH:MM’ format (eg, if the start of an AE date/time is 01MAY2019/08:00 and its recorded end date/time is 03MAY2019, then the maximum possible duration will be calculated by assuming the AE ended at the last hour and minute of 03MAY2019 [03MAY2019/23:59], thus will be presented as duration \leq 02:15:59 in the listing).
- For the calculation of summary statistics: If the severity of a TEAE is missing, a TEAE will be counted under the maximum severity possible.
- For the calculation of summary statistics: If a subject experienced multiple TEAEs with the same PT for the same treatment, this will be counted as 1 TEAE for that treatment under the maximum severity recorded.

